### 5.3 Appendix C: Imputation Rules for Missing Dates

#### Incomplete diagnosis or treatment date

- If day is missing, day will be set to 15th of the month.
- If month and day are missing, month and day will be set to July 1st.
- If year and month and day are missing, date will be set to missing.

#### Adverse Event

- If onset date is completely missing, onset date is set to date of first dose.
- If (year is present and month and day are missing) or (year and day are present and month is missing):
  - If year = year of first dose, then set month and day to month and day of first dose
  - If year < year of first dose, then set month and day to December 31st.
  - If year > year of first dose, then set month and day to January 1st.
- If month and year are present and day is missing:
  - If year=year of first dose and month = month of first dose then set day to day of first dose date month < month of first dose then set day to last day of month > month of first dose then set day to first day of month
  - If year < year of first dose then set day to last day of month
  - If year > year of first dose then set day to first day of month
- For all other cases, set onset date to date of first dose.

#### Concomitant Medications

- If start date is completely missing, start date will not be imputed.
- If (year is present and month and day are missing) or (year and day are present and month is missing), set month and day to January 1.
- If year and month are present and day is missing, set day to 1st day of month.
- If end date is completely missing, end date will not be imputed.
- If (year is present and month and day are missing) or (year and day are present and month is missing), set month and day to December 31.
- If year and month are present and day is missing, set day to last day of the month.

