#### 1.6.5 Safety Endpoints

The safety endpoints include frequency, intensity, and relationship to study drug of adverse events and serious adverse events, concomitant medications, and change from baseline in the following assessments:

- Physical examinations;
- Vital sign measurements;
- 24-hour ambulatory blood pressure monitoring (ABPM);
- 12-lead electrocardiograms;
- Clinical laboratory measurements;
- Weight.

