### 3.4.3 Concomitant Medications

The WHO Drug Dictionary will be used to classify all medications recorded during this study. Medications taken from 28 days prior to the administration of the first dose of bardoxolone methyl/placebo through the final follow-up visit will be recorded in the concomitant medication forms. The numbers and percentages of patients who had taken any baseline concomitant medications (i.e., start date on or before study Day 1 and stop date after Day 1) will be summarized by medication for each treatment arm. The numbers and percentages of patients who had started taking any post-baseline concomitant medications during Part 1 (i.e., start date after study Day 1 through Week 16) will be summarized by medication for each treatment arm. Study medications with start date after Week 16 will be excluded from the Part 1 summaries of concomitant medications, unless the patient did not continue into Part 2.

In the presence of partial dates, the available data (month and/or year) will be compared to the appropriate study reference dates to identify the most likely study period.

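### The SAP has two unreconciled rules for partial medication start dates, and the Appendix C rule can date a drug started on treatment to on or before Day 1

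*SAP*

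**What the plan says.** Concomitant medication is among the safety endpoints in SAP 1.6.5, which lists "adverse events and serious adverse events, concomitant medications, and change from baseline in the following assessments". SAP 3.4.3 defines two Part 1 tables by arm. A baseline drug has "start date on or before study Day 1 and stop date after Day 1". A post-baseline drug starts after Day 1 and by Week 16, with no condition on its stop date.

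The SAP gives two rules for incomplete medication dates:

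- **SAP 3.4.3, repeated in 3.5.3 for Part 2:** "the available data (month and/or year) will be compared to the appropriate study reference dates to identify the most likely study period".
- **SAP Appendix C, Concomitant Medications:** for a start date, "If year and month are present and day is missing, set day to 1st day of month"; where the month is missing, "set month and day to January 1"; and "If start date is completely missing, start date will not be imputed". For the end date, "If end date is completely missing, end date will not be imputed".

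SAP 3.7 allows partial dates of safety variables to be imputed, without requiring it, and points to Appendix C. It does not rank Appendix C against 3.4.3. The adverse-event rule in the same appendix does compare the partial date with first dose; the medication rule does not.

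**The concern.** The post-baseline table turns on one comparison: is the start after Day 1? Appendix C always moves an incomplete start to the earliest date compatible with what was recorded. For a drug truly started on treatment, the error can therefore go only one way, towards pre-treatment. The calendar month that contains Day 1 is where this happens with day-missing dates. Protocol 5.1.2 places the excess fluid-overload risk in the first three to four weeks of treatment, so new medication in that period is of particular interest.

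The reference-date rule in 3.4.3 might avoid the error, but it gives no answer for a start in the same month as first dose. Two programmers could follow the SAP and produce different tables.

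A second gap lies in the baseline definition. It asks for a stop date after Day 1, a fully missing end date stays missing, and no sentence says that a drug still being taken meets the condition.

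**Working it through.** The documents state no figure on this point, so there is none to reproduce. The check applies the rules literally.

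**Example records, Day 1 = 10 March 2017, Appendix C governing**

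| Record | Start used | Table under 3.4.3 |
|---|---|---|
| Start 20 March, complete, ongoing | 20 March | Post-baseline (correct) |
| True start 20 March, recorded as March 2017, stopped 30 April | 1 March | Baseline (wrong) |
| Same start, ongoing | 1 March | Neither |
| Recorded as April 2017, ongoing | 1 April | Post-baseline (correct) |
| Started on treatment, recorded as 2017 only, ongoing | 1 January | Neither |
| Start complete, in 2015, ongoing | as recorded | Neither, if ongoing drugs are not counted |

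The last row is the separate ongoing-drug gap. It concerns the baseline table only.

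**Share of partial on-treatment starts that are moved**

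Assumptions: Day 1 falls evenly on the 1,461 dates of 2014 to 2017, and true starts fall evenly on the N days after Day 1. A day-missing start is moved when the 1st of its month is on or before Day 1. A year-only start is moved when 1 January of its year is on or before Day 1. Share = moved combinations / (1,461 × N).

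- Day missing, N = 28: 21,420 / 40,908 = 52.4%.
- Day missing, N = 112: 21,520 / 163,632 = 13.2%.
- Year only, N = 28: 39,284 / 40,908 = 96.0%.
- Year only, N = 112: 138,320 / 163,632 = 84.5%.

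Counting study Days 2-28 and 2-112 instead (27 and 111 days) gives 54.0% and 13.3% for day-missing starts.

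**Share of all new Part 1 starts lost**

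The rate of partial dates is not in the documents. If a fraction p of new starts lacks the day, the loss is p × 13.2%:

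- p = 1%: 0.13%
- p = 5%: 0.66%
- p = 10%: 1.3%
- p = 20%: 2.6%

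Each 1% of new starts recorded by year only would lose 1% × 84.5% = 0.85%.

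**Week 16 boundary**

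SAP 3.5.5 counts a drug in Part 2 only if its first dose is after the Week 16 visit. A former placebo patient's drug begun soon after switching to bardoxolone methyl, with the day missing and the month being that of Week 16, is set to the 1st of that month. It can then be dated before the visit and counted in the placebo arm's Part 1 table.

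**Would the adverse-event rule do?**

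That rule sets a same-month onset to the first-dose date. A medication dated to Day 1 still starts on or before Day 1, so it would still not be post-baseline.

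**The case against.** The case for leaving this alone has several sound parts.

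- Only incomplete dates are touched. Concomitant medication is reviewed at every scheduled contact (Protocol Tables 3 and 4, including Days 3, 7, 10, 14, 21 and 28), and Protocol 9.10.4 requires changes to be recorded. Incomplete dates should be least common just after Day 1, and year-only dates rarer still. This stands, and it is why the 96% and 85% figures carry little weight.
- SAP 3.4.3 has its own rule, so Appendix C may never be applied to these tables. This stands in part: the loss is conditional on Appendix C governing. But the SAP does not say that it does not, and the 3.4.3 rule leaves a same-month start undecided.
- Other routes keep much of the information. Diuretic dose changes go in the eCRF (Protocol 9.3.2), adding a listed PAH therapy is a clinical worsening criterion (Protocol 9.10.32), and all eCRF data are listed by patient (SAP 2.3). This stands, although none of it corrects the by-arm table.

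A reader might infer that the rules turn on-treatment drugs in general into pre-treatment drugs, or that the endpoint misses new diuretics and PAH therapies. The documents do not support that. Complete dates and day-missing dates in a later month are sorted correctly, and no drug class is singled out. Nor does the ongoing-drug gap hide new starts, because the post-baseline definition has no stop-date condition. It also does not remove background PAH therapy from the report: SAP 3.3 separately summarises baseline PAH medications by arm. The gap is missing wording, not a stated exclusion.

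**Conclusion.** The point holds as a minor defect. The SAP has two partial-date rules for medications with no order of precedence. If Appendix C is applied, true on-treatment starts with a partial date in the month of Day 1 (or its year, if the month is missing) are dated on or before Day 1 and drop out of the post-baseline table. Among day-missing starts this is about 52% in the first 28 days and 13% over Part 1, assuming Day 1 and starts are evenly spread. At an assumed 5-10% of new starts without a day, it is about 0.7-1.3% of new Part 1 starts.

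The Part 1 figure is the relevant one. Multiplying the 28-day share by the same 5-10% gives about 3-5% of first-month starts, but the SAP plans no first-month medication table. A reader might also expect a false baseline imbalance between arms. Nothing in the documents shows one, and at these rates it would be small. The summaries are counts and percentages in a study that SAP 1.9 calls exploratory.

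The ongoing-drug wording is a separate clarification, confined to the 3.4.3 baseline table.

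**What to change.** 1. State in SAP 3.4.3, 3.5.3 and 3.7 that one rule governs partial medication dates, and delete the other.
2. In Appendix C, when a partial start falls in the same month as first dose (or the same year, if the month is missing), check the Screening and Day 1 medication record. If the drug is on it, treat it as baseline. If not, set the start to the day after first dose. State which eCRF entries make up that record, since the SAP does not define such a field. Do not copy the adverse-event rule, for the reason shown above.
3. Apply the same logic at the Week 16 visit for Part 2.
4. In 3.4.3, define a baseline drug as one started on or before Day 1 that is ongoing or has a stop date after Day 1.

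The cost is a few sentences and a small programming change. No new data are needed, because Protocol Tables 3 and 4 already schedule medication review at Screen A and Day 1. The downside is that a few drugs started just before Day 1 but not recorded then may be counted as new, in both arms alike.
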